5.5 Treatment exposure and compliance

RhC1-INH (Ruconest®) will be supplied by the production company Pharming Technologies, B.V., the Netherlands. RhC1-INH is a recombinant analogue of human C1-INH for intravenous injection. The primary and secondary structures of the molecule and target protease selectivity are consistent with those of plasma-derived C1-INH. RhC1-INH is purified from the milk of transgenic rabbits, and supplied as a sterile, preservative-free, white/off-white lyophilized powder for reconstitution for injection. RhC1-INH contains less than 0.002% of rabbit-related impurities. One international unit (U) of rhC1-INH activity is defined as the equivalent of C1-INH activity present in 1 mL of pooled normal plasma. Each vial of RhC1-INH contains 2100 U of rhC1-INH, 937 mg of sucrose, 83.3 mg of sodium citrate dihydrate and 1.0 mg of citric acid monohydrate. After reconstitution with 14 mL of sterile water for injection, each vial of rhC1-INH contains 150

	Trial Substance:	Ruconest®	Study No.: C1 6201 PROTECT-COVID-19-US
	Short Title:	Ruconest®: Prevention of severe SARS-CoV-2 infection in hospitalized patients with COVID-19	Sponsor: Pharming Technologies B. V.

U of rhC1-INH per 1 mL in a 20 mM sodium citrate buffer with a pH of 6.8. rhC1-INH does not contain preservatives and each vial is for single use only. After randomization, a pharmacist will open the respective sealed boxes, will reconstitute the respective number of rhC1-INH vials and prepare the study medication. RhC1-INH is for intravenous use only. The reconstituted solution is administered as a slow intravenous injection over approximately five minutes. Recommended doses of rhC1-INH for the treatment of an acute angioedema attack are 50 U/kg if body weight <84 kg and 4200 U if >84 kg. A second dose may be administered at the same recommended dose level within a 24-hour period. In this study, we will not use the product according to the licensed indication.

RhC1INH will be administered (150 U/ml) at a 50 U/kg dose (max dose of 4200 U) as a slow i.v. injection every 12 hours for 4 days: a total of 8 doses will be administered.

A market batch will be used for the study.

Participants in the control arm will receive SOC treatment according to local guidelines.

RhC1-INH syringes for all administration time points on a given day will be prepared by the pharmacist. The study drug including the exact time for administration of the first and subsequent syringes will be entered into the electronic prescribing system/chart or added to the paper chart. As this study involves IV administration of the IMP by nurses, patient compliance measures are not necessary. IMP will be administered by a nurse according to the site's standard procedures. Two nurses will check the IMP with respect to dose, study number and patient's identity before administration to the patient. Nurses will document the syringe number and the time of administration in the electronic or paper chart.

5.6 Derived variables

For quantitative variables the absolute changes from baseline (Visit 2) will be determined.

5.7 Withdrawal/discontinuation

Subjects may voluntarily withdraw from study participation at any time without having to provide a reason. Subjects may be withdrawn because of the appearance of a new health condition requiring care or medications prohibited by the protocol, unacceptable adverse event, refusal to continue treatment, or at the Investigator's discretion if it is in the subject's best interest.

A subject who withdraws informed consent before randomization or who develops a violation of the selection criteria before randomization is defined as a screening failure. No follow-up of screening failures will be performed.

Participants who withdraw informed consent, who do not fulfil inclusion/exclusion criteria after obtaining informed consent or who are diagnosed with an alternative disease (e.g. influenza infection) AND have not received any study medication will be withdrawn from the study.

Participants who experience a type I allergic reaction after any dose of study medication will be discontinued from further study interventions. Withdrawn or discontinued participants will not be replaced. Follow-up for all patient groups will be explained in Section 8.5 of the Clinical Study Protocol.

	Trial Substance:	Ruconest®			Study No.: C1 6201 PROTECT-COVID-19-US		
	Short Title:	Ruconest®: Prevention of severe SARS-CoV-2 infection in hospitalized patients with COVID-19			Sponsor: Pharming Technologies B. V.		

5.8 Schedule of assessments

The following table shows the study schedule of the clinical trial.

Table 1: Study schedule

Study Periods	Screening	Intervention Period					Follow-up	
Visit	1	2	3	4	5	6	7	
Time (weeks or days, or hours)	d-1 ¹	d0	d1	d2	d3-13 during admission	d14 (±2 d) or discharge	wk+4 (+3 months) ⁹	
In-/Exclusion Criteria	x							
Patient Information and Informed Consent	x							
Randomization		x						
Demographics	x							
Medical History	x							
Physical Examination	x	x	x	x	x	x	x	
Vital Signs including Respiratory Rate ⁷		x	x	x	x	x		
Laboratory Tests (blood) ³		x	x	x	x	x		
Virology testing		x ²			x ²	x ²		
Administer Study Medication ⁴		x	x	x	x			
Assessment of WHO ordinal scale		x	x	x	x	x	x	
Assessment of ICU admission and/or mechanical ventilation		x	x	x	x	x	x	
Measure Oxygenation levels ⁸		x	x	x	x	x		
Monitoring QT intervals ¹⁰		x	x	x	x	x		
Prior/Concomitant Medications	x	x	x	x	x	x	x	
Laboratory assessment in detail:								
Routine full blood count ³		x	x	x	x	x		
Routine coagulation studies ³		x	x	x	x	x		
Routine biochemistry including LDH ³		x	x	x	x	x		
Serum pregnancy test	x ⁵							
Ferritin, IL-6, D-Dimer ³		x	x	x	x	x		
C1INH concentration ⁶		x	x	x	x	x		
C1INH activity ⁶		x ⁷	x ⁷	x ⁷	x ⁷			
Complement proteins (e.g. C3, C4) ³		x	x	x	x	x		
Blood volume (mL), total/study specific	0/0	15/5	15/15	15/5	15/5	15/15		
(Serious) Adverse Events	x	x	x	x	x	x	x	

¹Eligibility criteria to be assessed within 48 hours upon hospital admission.

²Inclusion of patients based on suggestive clinical symptoms and results from radiological studies will be possible. However, a nasopharyngeal swab for PCR validation of confirmed SARS-CoV-2 infection must be performed in all subjects no later after inclusion of the patients if not already performed before inclusion into the study. Subsequent virological testing for SARS-CoV-2 will be performed on day 4-7 (according to local standard) and again on day 14 if participants are still admitted.

³Routine laboratory tests will be performed once before 1st administration of study medication on (day 0 through day 3) and once daily during hospital admission according to standard procedures of the study site, but will include a set of hematology, coagulation and biochemistry parameters. Additional blood samples will be collected at the same time.

⁴IMP will be administered every 12 hours for 4 days. A total of 8 doses will be administered. Trial medication will be stopped in participants in whom PCR results are not consistent with confirmed COVID-19 and in patients that are discharged or transferred to another facility.

	Trial Substance:	Ruconest®	Study No.: C1 6201 PROTECT-COVID-19-US
	Short Title:	Ruconest®: Prevention of severe SARS-CoV-2 infection in hospitalized patients with COVID-19	Sponsor: Pharming Technologies B. V.

⁵A Serum hCG pregnancy test will be performed in women who may become pregnant, are sexually active, and do not use adequate contraceptive measures.

⁶Collection of samples will be once daily before 1st administration of study medication (day 0 through day 3) and once daily until hospital discharge.

⁷The worst value recorded on a given day will be documented.

⁸Oxygenation levels will be measured for patients on oxygen while hospitalized.

93-months follow-up period begins post-treatment (Day 0). Assessments will be done daily until discharge and weekly via telemedicine interview or telephone call post-discharge.

¹⁰Monitoring of prolonged QT intervals in severely-ill subjects receiving multiple drugs.

6 SAMPLE SIZE

This is a pilot study investigating the efficacy and safety of rhC1-INH in the prevention of clinical deterioration in a high-risk population with COVID-19. There is no reliable information available on the clinical evolution of the population included in the trial. Therefore, a precise quantitative pre-definition of the sample size of a population needed to obtain clinically significant primary endpoint is not possible at this point in time.

The assumptions which are proposed and the criteria to monitor and assess the primary endpoint are as follows:

The primary endpoint is a 7-point scale and the standard deviation σ can be expected as 1.5 points. A relevant effect δ is an advantage of at least 1 point. Then, the standardized difference is about $\delta/\sigma = 0.67$. For a fixed sample size design with a two-sided significance level of $\alpha = 0.05$ and a power of $1 - \beta = 0.80$, a sample size of $N = 2 \times 38$ is necessary. Because of a nonparametric test, we add 4 patients in each group, and because of drop-outs we add also 4 patients in each group to $N = 2 \times 46$. For a 2:1-randomization, a nonparametric analysis by the stratified Wilcoxon rank-test, and an adaptive group sequential analysis, the overall sample size is estimated as $120 = 80 + 40$.

All patients are hospitalized, and it is very unlikely that the primary endpoint at Day 7 will not be measured. Nevertheless, a drop-out rate of about 10% is included.

Adaptive design:

Two interim analyses after 40 and 80 patients are planned according to the Pocock adjusted levels $\alpha_p = 0.0221$. Based on the results of an interim analysis the sample size can be adjusted (Lehmacher, Wassmer, 1999). There are no prespecified futility margins, but the DSMB can recommend stopping the study in the case of insufficient interim results.

The primary efficacy endpoint and the main secondary efficacy endpoints will be analyzed at latest at 14 days after start of treatment.

7 DATA ENTRY AND VALIDATION

The data entry of all records documented in the CRFs is carried out by two independent data entry persons and result in two different data sets, which will be compared. The double-entered CRF-database will be corrected until conformity is proved. Furthermore, the data will be analyzed for completeness and several plausibility checks will be carried out.

	Trial Substance:	Ruconest®	Study No.: C1 6201 PROTECT-COVID-19-US
	Short Title:	Ruconest®: Prevention of severe SARS-CoV-2 infection in hospitalized patients with COVID-19	Sponsor: Pharming Technologies B. V.

8 COMPUTER SYSTEMS, SOFTWARE, AND VALIDATION OF PROGRAMS

8.1 Hardware

Hardware used at CRMB is:

- Network servers:
FSCTX300S4, Raid 5, 4 x 146 GB Sas HDs, 16 GB Ram
- Desktops (workstations):
7 Desktops based on AMD and Intel
- Scanners:
F-Secure Antivirus 7.0 for Windows Server
ESET NOD 32 Antivirus Version 9 is used on the desktops
- Backup method:
On every Friday a full backup with Acronis True Image Echo for Windows Server is performed (system and data). For the rest of the week a differential backup is created. The backups are stored on internal (RAID 5) and external hard discs. A complete backup can be reimported using Veem.

8.2 Software

Software used at CRMB is:

- DMSys from Sigmasoft, Version 5.1,
- SAS Version 9.4,
- Windows Server 2019 Network servers,
- Windows 10 on Workstations,
- Microsoft Office 365 for reports, tracking of CRFs.

The data management is performed using the validated Data Management System DMSys, Version 5.1, and the statistical analysis is performed using the validated statistical analysis program SAS, Version 9.4 under Windows 10.

8.3 Validation of programs

All SAS programs start with a header in which the following information is contained:

- Name of the program,
- author,
- date of creation,
- used analysis DATA sets.

All tables, graphics and listings contain in footer the name of the program with which they were created, and the date of creation.

All formats will be filed in a permanent format catalogue.

All SAS programs will be checked by a second SAS programmer responsible for the quality control (QC). He/she will also check all LOG files for ERROR messages and WARNINGS. ERRORS must not occur. WARNINGS must be checked as to whether they lead to wrong results.

	Trial Substance:	Ruconest®	Study No.: C1 6201 PROTECT-COVID-19-US
	Short Title:	Ruconest®: Prevention of severe SARS-CoV-2 infection in hospitalized patients with COVID-19	Sponsor: Pharming Technologies B. V.

Furthermore, the SAS programmer responsible for the QC will check the tables, figures, and listing for completeness and consistency. The review will be documented on the Program Validation Form.

The biometrician responsible for evaluation will make sure that the specifications of planned analysis have been correctly converted in SAS programs.

Analyses will be carried out anticipating SDTM datasets.

8.4 Restitution of programs

All SAS programs used in the analysis as well as the OUTPUT (listings, tables) will be stored, and archived together with the source code of the programs at CRM Biometrics GmbH.

9 CODING

Concomitant medications will be coded by means of the Drug Reference List/Drug Dictionary (WHO-DD). Adverse events and diseases will be coded using MedDRA, respectively.

10 DATA CHECKS

Before starting the statistical analysis, plausibility checks will be performed. A detailed list of edit checks can be found in the Data Management Plan (DMP, Appendix 5).

11 QUERIES

After performing the plausibility checks and the comparisons of the two data entry databases, the errors of the data entry will be corrected. Queries/Data Clarification Forms will be generated in the case of inconsistencies or missing data in the CRF. According to the resolved queries, changes of the data will be performed in the Master file, if necessary. In the case of remaining unsolved queries, the Principal Investigator, the responsible statistician, the medical advisor and the project manager will decide how to handle these data and all decisions taken will be documented in detail.

12 BLIND REVIEW

A blind data review meeting will take place before closing the database. A listing of all protocol deviations with the proposed classification into minor and major protocol deviations and a list of all data irregularities or unresolved queries and a proposal for how the data are to be handled in the analysis, if necessary, will be provided in the Blind Review Meeting (BRM). At least the responsible biometrician and the Clinical Project Manager will sign the Blind Review Meeting Minutes.

13 DATABASE CLOSURE

After all queries have been replied, the database master file will be corrected, if necessary, and the decisions regarding the handling of the unresolved queries will be made, and the database will be closed.

	Trial Substance:	Ruconest®	Study No.: C1 6201 PROTECT-COVID-19-US
	Short Title:	Ruconest®: Prevention of severe SARS-CoV-2 infection in hospitalized patients with COVID-19	Sponsor: Pharming Technologies B. V.

14 STATISTICAL EVALUATION

14.1 General

All statistical analyses will be performed in accordance with the ICH E9 “Statistical Principles for Clinical Trials” guideline.

14.2 Datasets to be analyzed, Analysis populations

A review of the database will be conducted in a blinded manner shortly before the database will be locked, and any decisions made at that meeting (blinded Data Review Meeting) concerning the statistical analysis, *e.g.*, additional outcomes and populations, pooling of sites for efficacy analysis, will be documented in the Statistical Analysis Plan (SAP).

Missing data for the primary endpoint will be imputed by means of the Last-observation-carried-forward (LOCF) method, as sensitivity analyses some alternative imputation methods like imputation of the mean and multiple imputation will be additionally performed.

The following analysis populations will be used for analysis of study data:

Safety population: The Safety Population is defined as all patients who received at least one dose of rhC1-INH. Statistical analyses will be based on the actual treatment the patient received.

Full Analysis Set (FAS)/Intention to treat (ITT) population: The FAS/ITT Population is defined as all patients who are randomly allocated to a study arm. Statistical analyses will be based on the treatment arm to which the patient was allocated. For quantitative data, the number of patients with non-missing information, means, medians, standard deviations and extremes will be determined. For qualitative data, absolute and relative frequencies will be calculated. Moreover, changes from baseline (V2, d0) will be calculated.

Per protocol (PP) population: The PP Population is defined as all patients in the FAS/ITT Population who complete the study and who do not have any major protocol violations, including the following:

- Patients who had major inclusion/exclusion criteria violations.

Sufficient compliance is expected because of IV administration of the IMP.

The PP Population will be determined by a blinded review in the Data Review Meeting (DRM) of the data prior to database lock. The primary efficacy analysis will be based on the FAS/ITT Population in this superiority trial; an additional efficacy analysis will be performed on the PP Population. The Safety Population will be used for all safety analyses.

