Statistical Considerations:	
Detailed methodology for statistical analyses of the data collected in this trial will be documented in a Statistical Analysis Plan.
 
Full Analysis Set/Intent-to-Treat Population: The FAS/ITT Population is defined as all patients who are randomly allocated to a study arm. Statistical analyses will be based on the treatment arm to which the patient was allocated.
 
Safety Population: The Safety Population is defined as all patients who received at least one dose of rhC1INH.
 
The primary endpoint WHO 7-point outcome scale at day 7 will be analyzed by means of the nonparametric Wilcoxon rank test stratified by its baseline values with two-sided α-level of 5 %.
 
The secondary endpoint is time to improvement of at least 2 points. It will be tested only after a significant test of the primary endpoint (a priori ordered hypotheses), therefore, no alpha adjustment is necessary.
 
Furthermore, 95% confidence intervals will be determined, and the results will be presented graphically by means of box-and-whisker plots.
 
Time to event (e.g. death, virological clearance, defervescence) will be displayed by Kaplan-Meier plots and compared with a Wilcoxon rank test. Appropriate statistical tests will be used for the analysis of other outcomes of interest and will be detailed in the statistical analysis plan prior to unlocking of the study database.

GCP Statement:	This study will be conducted in compliance with the protocol, the Sponsor's standard operating procedures and/or guidelines, the United States Food and Drug Administration (FDA) regulations, the current version of the Declaration of Helsinki, the International Conference on Harmonization (ICH) GCP guidelines and other local regulations, as applicable.
-----------------------	---

ABBREVIATIONS

Provide a list of abbreviations used on the protocol - to be completed

AE	Adverse Event
ALI	Acute lung injury
C1-INH	C1 inhibitor, C1 esterase inhibitor
COVID-19	Coronavirus disease 2019
CRF	Case Report Form (Paper)
CS	Complement system
CTCAE	Common terminology criteria for adverse events
DSUR	Drug safety update report
EMA	European Medicines Agency
FDA	Food and Drug Administration
GCP	Good Clinical Practice
HAE	Hereditary Angioedema
Ho	Null hypothesis
H1	Alternative hypothesis
HRI	Host-Related Impurities
IB	Investigator's Brochure
IC	Informed Consent
ICU	Intensive Care Unit
IME	Important Medical Event
IMP	Investigational Medicinal Product

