3.6 Explanation for Choice of Comparator

Currently, no approved or effective treatment options for COVID-19 infections exist. Participants will either receive rhC1INH plus SOC or only SOC. SOC may include treatment for underlying comorbidities and management of COVID-19 symptoms. Importantly, local treatment protocols including drugs with perceived benefits in COVID-19 infections such as lopinavir/ritonavir are allowed as long as they are declared as SOC. In order to facilitate patient recruitment in a time of restricted human and financial resources, and because of an objective primary endpoint, a placebo group will be omitted.

Diphenhydramine, hydroxychloroquine, and azithromycin are associated with prolongation of the cardiac QT interval, and subsequent increased risk of fatal cardiac arrhythmia.

Cardiovascular monitoring will be conducted in severely-ill subjects receiving multiple drugs on a case-by-case adjudication of any prolongation of QT intervals to evaluate the benefit-risk of continued participation in the clinical study.

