5.4 Safety Outcomes

The study will evaluate the safety of rhC1INH in the setting of COVID-19 infections if added to SOC compared to SOC treatment only by measuring the incidence of adverse events up to 3 months post-treatment.

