8.1.2 Control Intervention (standard/routine/comparator treatment / medical device)

Participants in the control arm will receive SOC treatment according to local guidelines.

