11.4 Planned Analyses

11.4.1 Datasets to be Analysed, Analysis Populations

A review of the database will be conducted in a blinded manner shortly before the database will be locked, and any decisions made at that meeting (blinded Data Review Meeting) concerning the statistical analysis, e.g., additional outcomes and populations, pooling of sites for efficacy analysis, will be documented in the Statistical Analysis Plan (SAP).

Missing data for the primary endpoint will be imputed by means of the Last-observation-carried-forward (LOCF) method, as sensitivity analyses some alternative imputation methods like imputation of the mean and multiple imputation will be additionally performed.

Safety Population: The Safety Population is defined as all patients who received at least one dose of rhC1INH. Statistical analyses will be based on the actual treatment the patient received.

Full Analysis Set/Intent-to-Treat Population: The FAS/ITT Population is defined as all patients who are randomly allocated to a study arm. Statistical analyses will be based on the treatment arm to which the patient was allocated. For quantitative data, the number of patients with non-missing information, means, medians, standard deviations and extremes will be determined. For qualitative data, absolute and relative frequencies will be calculated. Moreover, changes from baseline (V2, d0) will be calculated.

Per Protocol Population: The PP Population is defined as all patients in the FAS/ITT Population who complete the study and who do not have any major protocol violations, including the following:

- Patients who had major inclusion/exclusion criteria violations.

Sufficient compliance is expected because of IV administration of the IMP.

The PP Population will be determined by a blinded review in the Data Review Meeting (DRM) of the data prior to database lock. The primary efficacy analysis will be based on the FAS/ITT Population in this superiority trial; an additional efficacy analysis will be performed on the PP Population. The Safety Population will be used for all safety analyses.

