11.4.5 Safety Analysis

The assessment of safety will be based mainly on the frequency of adverse events (AEs) that are treatment-emergent (TEAEs). Formal tests will not be conducted for differences in safety parameters between treatment groups.

The incidence of all treatment-emergent AEs will be tabulated after grouping by system organ class and preferred term. For each preferred term and summarized over each system organ class overall, the table will present the absolute number and proportion (%) of patients in each treatment group in whom the event occurred. The incidence of all suspected-IMP-related AEs will be tabulated similarly. The incidence of all treatment-emergent AEs will also be tabulated by severity categories.

Safety will also be summarized with respect to vital signs as mean levels by visit and change from baseline. Abnormal observations on physical exams will be listed.

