5.3 Safety variables

The study will evaluate the safety of rhC1-INH in the setting of COVID-19 infections if added to SOC compared to SOC treatment only by measuring the incidence of adverse events up to 3 months post treatment. Moreover, vital signs, physical examinations, and laboratory variables will be assessed for safety.

- Adverse events.
- Physical examination.

	Trial Substance:	Ruconest®	Study No.: C1 6201 PROTECT-COVID-19-US
	Short Title:	Ruconest®: Prevention of severe SARS-CoV-2 infection in hospitalized patients with COVID-19	Sponsor: Pharming Technologies B. V.

A brief, general physical examination will be performed at all visits. Examination will include: height, body weight, eyes, ears/nose/throat, cardiovascular, respiratory, gastrointestinal, genitourinary, musculoskeletal, neurological and psychiatric according to the state of the art.

- Vital signs.

Vital signs will be measured at Visit 2, 3, 4, 5, and 6:

- Heart rate
- Respiratory rate
- Temperature
- Blood pressure (BP_s, BP_d)
- SpO₂.

- Pregnancy.

A serum hCG pregnancy test will be performed at screening in women who may become pregnant, are sexually active, and do not use adequate contraceptive measures.

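### The Safety Population admits only patients dosed with rhC1INH, so the planned adverse-event comparison with standard of care alone has no control patients in it

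*SAP*

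**What the plan says.** SAP 14.2 gives the definition: "The Safety Population is defined as all patients who received at least one dose of rhC1-INH". Protocol 11.4.1 and the Statistical Considerations in the synopsis carry the same sentence: "The Safety Population is defined as all patients who received at least one dose of rhC1INH". Protocol 11.4.1 then states: "The Safety Population will be used for all safety analyses". SAP 14.2 repeats this. Both sections add that patients in the set are analysed by the treatment they actually received.

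The control arm is described in protocol 8.1.2: "Participants in the control arm will receive SOC treatment according to local guidelines". Protocol 3.6 explains that "a placebo group will be omitted".

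The safety outcome in protocol 5.4 is nevertheless comparative. It concerns rhC1INH "if added to SOC compared to SOC treatment only by measuring the incidence of adverse events up to 3 months post-treatment". SAP 5.3 has the same outcome. For the adverse-event tables, protocol 11.4.5 says that "the table will present the absolute number and proportion (%) of patients in each treatment group in whom the event occurred", and SAP 14.6 and 14.6.1 repeat it. SAP 14.3 also plans a baseline summary of the Safety Population by treatment group. SAP 2 plans about 120 patients, 80 on rhC1INH and 40 on SOC.

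**The concern.** The definition suits a trial in which every patient receives a study product. Here one arm receives none, so the entry condition removes the whole comparator from the set that must serve every safety analysis.

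What is at stake is the ability to read adverse events against the background of the disease. Headache is the most frequent treatment-emergent event listed for rhC1INH (11%, protocol 3.7), and SAP 5.4 lists it among the signs and symptoms of COVID-19 to be recorded. Headache present before consent is medical history under protocol 9.1.4.1, but new or worsened headache is an adverse event in either arm. Thrombotic and thrombo-embolic events are singled out in protocol 10.1.4. Neither kind of event is an efficacy outcome in protocol 5.2 or 5.3. Without an SOC column, the tables cannot show whether such events are more or less frequent with rhC1INH than without it.

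**Working it through.** **Step 1: the planned group sizes.** The stated base is 38 per group; a two-sample calculation with difference 1, SD 1.5, two-sided 0.05 and 80% power gives 36 (normal) or 37 (t-test), close to it. The additions give 38 + 4 + 4 = 46 per group, 92 in all. Allowing for 2:1 allocation, 92 × 9/8 = 103.5. Allowing for three equally spaced Pocock looks at 0.0221 (inflation 1.1656 at 80% power), 103.5 × 1.1656 = 120.6, against the stated 120. The last two factors are a reconstruction; the documents do not show them. Split 2:1, 120 gives 80 and 40.

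**Step 2: who is in the set as written.**

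| Patient | rhC1INH doses | In the set? | Column under the as-treated rule |
|---|---|---|---|
| Randomised to rhC1INH, dosed | at least 1 | yes | rhC1INH + SOC |
| Randomised to rhC1INH, never dosed | 0 | no | none |
| Randomised to SOC, treated as planned | 0 | no | none |
| Randomised to SOC, given rhC1INH in error | at least 1 | yes | rhC1INH + SOC |

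No row leads to an SOC-only column. With the planned numbers:

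- Patients in the set: about 80/120 = 66.7%.
- Patients outside it: about 40/120 = 33.3%, which is 40/40 = 100% of controls.
- SOC denominator: 0 instead of about 40, so SOC percentages are undefined.

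**Step 3: which outputs are affected.**

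- The adverse-event tables by group (protocol 11.4.5; SAP 14.6 and 14.6.1) and the safety outcome that they deliver (protocol 5.4; SAP 5.3) cannot be produced. This is one lost comparison.
- The Safety Population baseline summary (SAP 14.3) loses its SOC column, but the FAS summary in the same section shows both arms.
- The primary analysis uses the FAS/ITT set and is untouched. Mortality, ICU treatment, ventilation and ARDS are outcomes for both randomised arms (protocol 5.2 and 5.3) and remain available.
- The IMP exposure table (SAP 14.12) is properly limited to dosed patients.

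**Step 4: what the correction restores.** With about 80 and 40 patients, the half-width of a 95% interval for a difference in event proportions is 1.96 × √[p(1 − p)(1/80 + 1/40)]. If p is the same in both arms (assumed values), this is 11.4 percentage points at p = 0.10 and 17.4 at p = 0.30. The restored comparison is coarse, but it is the one the plan promises.

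**The case against.** The strongest reply is that this is a drafting slip with an obvious intention. The as-treated sentence has little purpose in a one-treatment set, the tables refer to each treatment group, and SAP 14.3 allows for the Safety set being the same as the FAS, which a set without controls never could be. Safety is descriptive, with no formal tests, in a pilot trial. The SAP is finalised only after the blind review (SAP 1), and the Data Review Meeting may add populations (SAP 14.2).

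Much of this stands: the intended comparison is clear, no hypothesis test is at risk, and there is still an opportunity to correct the text. It does not remove the problem. The as-treated rule sorts members of the set and admits no one. The Data Review Meeting option is discretionary, and no set containing SOC patients is specified. Nor does the intention settle the denominator: nothing says whether rhC1INH-arm patients who were never dosed count as SOC, and those withdrawn undosed are not followed up (protocol 8.5 and 9.1.5).

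A reader might infer more than the documents support. One inference is that, after the Day 28 outcomes end, the adverse-event tables are the only by-arm source on serious deterioration. They are not: Visit 7 assesses the WHO scale, ICU admission and mechanical ventilation in both arms for up to 3 months (protocol 9.1 and 9.2.1), and SAP 15 commits to analysing all data by scheduled visit. Another is that control-arm safety data are lost. They are not, because adverse events are recorded for all participants (protocol 9.1.4.1).

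**Conclusion.** The definition is wrong as written, identically in the SAP, protocol 11.4.1 and the synopsis, so no version corrects another. All of the roughly 40 planned controls fall outside the set required for every safety analysis, and the stated comparison of adverse-event incidence with SOC only cannot be produced under the plan's own rules.

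The finding rests on set membership and the planned 80:40 split, not on modelling. It assumes that controls do not receive rhC1INH, as the protocol intends; a control dosed in error would be counted with rhC1INH and would not create an SOC column. The damage is confined to a descriptive safety comparison and, to a minor degree, one baseline table. It should be corrected before the SAP is finalised, because in an open-label trial the safety denominator is better fixed in advance than at a meeting shortly before lock.

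**What to change.** In SAP 14.2, protocol 11.4.1 and the synopsis, define the Safety Population as randomised patients grouped by treatment received:

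- rhC1INH + SOC: received at least one dose of rhC1INH.
- SOC only: randomised to SOC, received no rhC1INH, and entered the Day 0 study period.

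Treat early withdrawals alike in both arms. List separately, outside the denominators, rhC1INH-arm patients who were never dosed and SOC patients withdrawn before the Day 0 start. Removing undosed rhC1INH patients while keeping SOC patients who left equally early could lower the SOC percentages. Because randomisation itself takes place on Day 0, the SAP should name the recorded event that marks entry to the Day 0 period for SOC patients.

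As a minor clarification, state in protocol 10.1.1 and SAP 14.6 that Day 0 (randomisation) is the treatment-emergent start for SOC patients, since protocol 10.1.1 ties it to first treatment. Keep the IMP exposure table limited to dosed patients.

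The cost is rewording in the SAP and the protocol, with the protocol change going through the normal IRB amendment process (protocol 2.2 and 2.8), plus table programming. No new data are needed.
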